Sample size determination. We will enroll 66 participants and expect 50 to complete the study. This drop-out rate accounts for participant non-compliance. In our previous Sleep Study, our completion rate was 90%. We expect a larger drop-out rate in the proposed study due to the longer duration of each treatment phase, and we also anticipate dismissing some participants due to non-compliance. Each participant will undergo 2 study phases, and each response variable will be measured at least once per phase. Thus, for each response measure we will have at least  $50 \times 2$  paired observations. We have analyzed preliminary data consisting of a number of measurements from 2 overweight women from our Pilot Study. Based on preliminary data analysis we have estimated an effect size (mean paired difference) of  $0.69 \pm 0.36$  g for fat mass and an effect size (mean paired difference) of  $0.91 \pm 0.65$  g for weight gain. This translates to very large effect sizes of 1.92 (fat mass) and 1.4 (weight gain) for paired t-tests. With these effect sizes we have more than 99% power for paired t-tests.] We have estimated the EI effect size to be  $295.9 \pm 116.3$  kcal [8]. The effect size for a paired t-test (effect size divided by the standard deviation) for a paired t-test is >2, which is a very large effect size for paired t-test. This means with  $50 \times 2$  paired samples, we have >80% power for paired t-test. In [name] et al. 2011 [8], we also reported an effect size of  $20.7 \pm 6.8$  g for fat intake and an effect size of  $57.9 \pm 32.6$  g for carbohydrate intake. This translates to very large effect sizes of 3.04 and 1.78, respectively for fat and carbohydrates for paired t-test. With these effect sizes we have >80% power for paired t-test. Moreover, using the R^2 value from our linear model analysis of [name] et al. 2011, we determined that we have >80% power for proposed linear mixed model analyses (as described in statistical plan) with energy balance, fat and carbohydrate intakes. Thus, we have very good power overall, which will be useful in our primary analyses as well as in exploring sex differences. Statistical plan. Exploratory data analyses for physiological, anatomical, biomarker and intakerelated responses will be performed using R, SAS and other software. As part of the analysis, we will compute descriptive statistics for each variable. In particular, we will compute the proportion, mean, variance, standard error and the range of continuous variables and frequency and mode for discrete variables. Descriptive statistics will be computed for each specific sleep phase. In addition, correlation coefficients between the variables will be computed and scatter plots will be checked for linear relationships. The correlations and scatter plots help assess the degree of collinearity among variables, which will be useful for interpreting regression-based linear mixed model analyses discussed later. The data will be tested for normality, and if needed an appropriate transformation will be used on the raw data to make the normal approximation better. We will have a comprehensive strategy to deal with missing data. We will study missingness to decide if the data are missing at random or missing completely at random. Missing rates will also be estimated for each variable. Missing values will be imputed, as appropriate. We will fit a linear mixed model to analyze the data. Treatments (sleep duration: SR vs. HS) will be fixed effects and subjects a random effect. As we are collecting data from two phases for each subject, we will test for carryover effects by using a treatment x phase interaction in an initial version of each linear model. If the interaction term is not significant then we will rebuild the linear model without the interaction term. The other independent variables (covariates) will be sex, age, baseline BMI, and race/ethnicity. If required anywhere in the analysis plan, p-values will be adjusted for multiple comparisons. Sp. Aim 1: Hypothesis 1a. SR will lead to increased total adipose tissue mass, as assessed using MRI, relative to HS. We will perform repeated measure linear mixed model analyses separately for adipose tissue mass increase and weight gain (as the response). Sleep duration (SR vs. HS) and the covariates will be used as independent variables. Subject will be used as a random effect. Paired t-test and Wilcoxon test will be used to determine whether the SR and HS have different

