
effects on weight gain and adipose tissue mass increase. Hypothesis 1b. EE, assessed by DLW, and physical activity level, monitored daily by actigraphy, will be lower during SR relative to HS. We will perform repeated measure linear mixed model analyses separately for DLW and actigraphy-derived variables as the responses. Sleep duration (SR vs. HS) and the covariates will be used as independent variables. Subject will be used as a random effect. Paired t-test and Wilcoxon test will be used to determine whether SR and HS have different effects on DLW and actigraphy measures. Sp. Aim 2: Hypothesis 2a. EI, assessed by [3-d food records], will be greater during a period of SR relative to HS. This will be mostly due to increased fat and carbohydrate intakes. We will perform a repeated measure linear mixed model analyses separately with each EI measure (as the response) and sleep duration (SR vs. HS) and the covariates as independent variables. Subject will be used as a random effect. Paired t-test and Wilcoxon test will be used to determine whether the SR and HS have different effects on EI measures. Hypothesis 2b. Neural responses to food stimuli, assessed by fMRI after 6 wk of SR or HS, will indicate increased activity in networks associated with reward and food valuation (insula, orbitofrontal cortex) during a period of SR relative to HS. These responses will be correlated with intakes of high carbohydrate and high fat foods (hypothesis 1a) and [ghrelin]. Connectivity of the networks involved in reward valuation at rest will be stronger after SR compared to HS and synchrony of the DMN will be reduced after SR compared to HS. Sp. Aim 3: Hypothesis 3a. SR will lead to [increased glucose, insulin, triglycerides, and reduced highdensity lipoprotein cholesterol and adiponectin relative to HS.] We will perform repeated measure linear mixed model analyses separately for each of glucose, insulin, triglycerides, high-density lipoprotein cholesterol and adiponectin. Sleep duration (SR vs. HS) and the covariates will be used as independent variables. Subject will be used as a random effect. One-sided paired t-test and Wilcoxon test will also be used to determine whether the SR and HS have different effects on the cardio-metabolic risk profiles, as well as the direction of the effects. Hypothesis 3b. Increased adiposity and poor diet quality (higher fat and carbohydrates) after SR will partially explain the adverse cardio-metabolic risk profile associated with SR. We will select the cardiometabolic risk profile variables that are adversely associated with SR. Then, we will compute the difference in those variables in SR vs. HS (i.e. the value of each variable in SR minus the value of that variable in HS). Using a linear model analysis, we will test if these differences are associated with increased adiposity and poor diet quality. If, for some variables, there are multiple observed differences for each subject then a linear mixed model analysis will be used with subject as a grouping variable. A separate analysis will be performed for each such difference, with the difference as the response variables and adiposity, food quality variables and the covariates as dependent variables. *Linear Mixed Model Analyses.* We will fit a linear mixed model to analyze the data. Treatments (SR vs. HS) will be used as fixed effects and subject will be used a random effect. The other independent variables, such as demographic variables, will be covariates. Those covariates will be removed if they do not significantly contribute to the model. Aim 4: (To determine whether long-term mild SR, relative to HS, challenged acute cognitive outcomes in older and younger adults. Hypothesis 4a. Mild SR will induce cognitive decline, assessed using with the NIH Toolbox, which will be greater in older relative to younger adults.) Outcomes are measures from the NIH Toolbox. Each outcome will be analyzed in separate linear mixed model analyses, for older and young participants, as detailed in "*Linear Mixed Model Analyses*" section above. Sleep (SR vs. HS), along with phase (1 vs. 2), carryover effects, and covariates (if they are found to be significant in an initial analysis) will be used in the model. Subject will be used as a random effect. Then, we will pool the datasets to include both older and young participants. In the pooled dataset, we will use the average differences in NIH Toolbox measures (from HS to SR) as outcomes in linear model analysis. Age group (older vs. younger) will be used as main predictor variable. We will also apply covariates as independent variables, if they are found to be significant in an initial analysis. We will use unpaired t-test on the average difference in

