
NIH Toolbox measures (from HS to SR), to test if these values are significantly different between older and young participants. Aim 5: (To determine whether the effects of SR on cognitive outcomes are moderated by brain atrophy in younger and older adults. Hypothesis 5a. The effect of mild SR on cognition will be greater among individuals with greater amounts of cortical thinning, smaller hippocampi, and greater WMH volume. This effect will be greater in older relative to younger adults.) Separately for older and young participants, we will perform linear model analyses, with average differences in NIH Toolbox measures (from HS to SR) as outcomes (separately for each outcome). Cortical length, hippocampi size and WMH volume will be used as independent variables. We will apply covariates as independent variables, if they are found to be significant in an initial analysis. Then, we will pool the datasets to include both older and young participants. In the pooled data, we will perform linear model analyses, with average differences in NIH Toolbox measures (from HS to SR) as outcomes. Cortical length, hippocampi size, WMH volume and age group (older vs. younger) will be used as independent variables. We will also use covariates as independent variables, if they are found to be significant in an initial analysis. Aim 6: (To determine whether changes in metabolic or hormonal profiles mediate changes in cognitive function as a result of SR. Hypothesis 6a. The effect of mild SR on cognition will be mediated by changes in hormones (leptin, adiponectin, and insulin).) Separately for older and young participants, and separately for each hormone measure, each outcome (from NIH toolbox) will be analyzed with mediation analysis (Baron and Kenny's method). Sleep type (SR. vs HS) will be the predictor in the analysis. Hormone measure will be used as the potential mediator. As we have multiple measures from each participant, each component analysis in Baron and Kenny's method will be done as linear mixed model analysis, with subject as random effect. Within each mediation analysis, the first analysis will only have one fixed effect: sleep (SR vs. HS). The outcome measure will be the dependent variable. If sleep is found to be significant, then the second analysis will be done with the hormone measure as the dependent variable, and sleep as the fixed effect. If sleep is also found to be significant in the second analysis, then in the final analysis, the outcome measure will be the dependent variable. Fixed effects will be sleep and the hormone measure. If the hormone measure is still found to be significant, and the coefficient of sleep has decreased in absolute value from the first analysis, then a mediation effect of hormone will be concluded.

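### The pooled older v younger models of Aims 4 and 5 admit covariates only if significant, which can leave confounding in a non-randomised contrast and can raise its error rate

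*Combined protocol and SAP*

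**What the plan says.** All of this is in the Statistical Procedures section of the combined protocol and SAP.

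- **Candidate covariates:** "The other independent variables (covariates) will be sex, age, baseline BMI, and race/ethnicity".
- **General rule (Linear Mixed Model Analyses paragraph):** "Those covariates will be removed if they do not significantly contribute to the model". The text for Aims 1 to 3 enters the covariates without any such condition, so the two statements do not sit well together.
- **Aim 4, pooled model:** the outcome is each person's average change in an NIH Toolbox measure from habitual sleep (HS) to sleep restriction (SR). "Age group (older vs. younger) will be used as main predictor variable", and "We will also apply covariates as independent variables, if they are found to be significant in an initial analysis".
- **Aim 4, second test of the same contrast:** "We will use unpaired t-test on the average difference in" the Toolbox measures. This test has no covariates.
- **Aim 5, pooled model:** "We will also use covariates as independent variables, if they are found to be significant in an initial analysis".
- **Multiplicity:** "If required anywhere in the analysis plan, p-values will be adjusted for multiple comparisons".

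The plan does not define the initial analysis or its threshold, and does not say whether selection is repeated for each outcome. It names neither the linear model nor the t-test as the main test of the age difference. Continuous age is in the candidate list, and Aims 4 and 5 do not take it out.

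**The concern.** In a crossover, each person serves as their own control, so sex, BMI or race/ethnicity can do little to the SR v HS contrast. The pooled Aim 4 and Aim 5 models are different. They reduce each person to one HS-to-SR difference and then compare people. Nobody is randomised to an age group, so covariate adjustment is the only planned protection against confounding.

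A significance rule is weak protection in a sample of this size, because a real confounder will often miss significance and be dropped. The p-value for age group is then read as if no selection had taken place. At stake is the second half of Hypothesis 4a, that decline is greater in older adults. An apparent age effect could partly reflect the sex, BMI or race mix of the two groups. The adjustment set could also change from one Toolbox outcome to the next.

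**Working it through.** **The plan's own figures.** The documents give no sample size, power or error rate for the older v younger contrast. The parent-study figures do reproduce: 0.69/0.36 = 1.92 and 0.91/0.65 = 1.40, with paired-test power above 99% at n = 50. They do not bear on this contrast.

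**Inputs from the documents.** 66 enrolled and 50 expected completers (Statistical Procedures); target accrual 79 and 36 completers to date (Subjects); ages 20-40 and 55-75.

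**Assumptions.** The size of the older group is not stated. 79 - 66 = 13 is one reading; at the planned completion rate, 13 × 50/66 = 9.8, or about 10. The splits 8 v 28 and 6 v 30 are guesses that add to the 36 completers. Covariate effects, imbalances, uniform ages within each range, and two-sided 0.05 for both selection and testing are also assumed. Effects and bias are in residual SDs of the person-level difference.

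**Step 1: what dropping a covariate does.** Write D = a + b·Old + Σ g_j·x_j + error. Dropping x_j shifts the estimate of b by the estimated g_j times the group difference in x_j. With three covariates and no adjustment, the bias is 3 × 0.20 × 0.5 = 0.30 SD at the low end and 3 × 0.25 × 0.8 = 0.60 SD at the high end.

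**Step 2: how often a real confounder is dropped.** With n = 60 the standard error of g is about 1/√60 = 0.129. Effects of 0.20 and 0.25 give z = 1.55 and 1.94, so the chance of reaching significance is about Φ(1.55 - 1.96) = 34% and Φ(1.94 - 1.96) = 49%. With n = 36 (standard error 0.167, z = 1.20 and 1.50) it is about 22% and 32%. Each confounder is therefore dropped in roughly half or more of trials.

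**Step 3: simulation with no true age effect.** Three covariates, effects 0.20-0.25 SD, continuous age not in the list, sizes 10 v 50, 13 v 50 and 8 v 28.

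| Setting | Drop if non-significant: error (bias) | Keep all: error (bias) |
|---|---|---|
| Balanced | about 5-6% (none) | about 5% (none) |
| 0.3 SD imbalances, or one covariate imbalanced | 7-8% (0.06-0.08 SD at 10 v 50) | about 5% (none) |
| All three imbalanced 0.5-0.8 SD, same direction | 9-17% (0.13-0.28 SD; 0.31 in one run at 8 v 28) | 4.5-6% (none) |

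Other runs at 13 v 50:
- One covariate correlated 0.2-0.4 with the outcome and imbalanced by 0.5-1 SD: 5.4-9.9%, bias 0.00-0.09 SD.
- Older group 10% women v 50% in the younger, sex effect 0.3-0.5 SD: 7.2-7.6%, bias about 0.07 SD.

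**Step 4: continuous age in the list.** Uniform ages have within-group variance 20²/12 = 33.3. With means of 30 and 65 and 13 of 63 people older, the between-group variance is (13/63)(50/63) × 35² = 200.6. So R² = 200.6/(200.6 + 33.3) = 0.858, correlation 0.93, and variance inflation 1/(1 - 0.858) ≈ 7. Dropping non-significant terms from that model gave 8.0-9.1% error with no confounding and 9.7-12.4% with it. Keeping every term held the nominal rate but was less precise.

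**Step 5: the other ways to test the contrast.** Univariable screening without age in the list gave 4.8-5.3% when only sex was imbalanced or nothing was, and 5.7-8.0% in the three-covariate case, where bias of 0.11-0.22 SD remained. With age in the list it was conservative (1.8-2.8%). The unpaired t-test in the three-covariate case gave 11-41% error and 0.30-0.61 SD bias.

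**Step 6: the randomised contrast.** With complete pairs, a mixed model with and without sex and BMI gave the same SR v HS estimate and standard error to five decimals.

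**The case against.** The strongest reply is that bias needs a covariate that both modifies the SR effect and differs between the age groups, and the documents establish neither. That stands. The Subjects section applies one BMI rule to both age groups, so a large BMI gap has no support in the text. The same section's reference to pre-menopausal women might lead a reader to infer an almost entirely male older group. But the recruitment text invites men and women aged 55-75, and the document list includes an older-adult advertisement for both sexes. The low-women scenario is therefore a possibility, not a finding.

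A second reply is that the initial analysis may mean univariable screening, which inflates error little. That also stands for the error rate. It does not stand for bias, which remains when covariates are imbalanced. That the plan leaves the procedure open is itself part of the problem.

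A third is that the selected model is less biased than the unadjusted t-test planned alongside it. True, but neither is named as the main test, so the t-test does not rescue the contrast.

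Finally, the study is in data analysis and a cognitive paper is in press, so a change of wording alone will not reach every result. This affects how the fix is reported, not whether it is worth making.

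**Conclusion.** The concern holds in a limited form. The significance rule can leave confounding in the older v younger contrast and can raise its error rate. A reader might infer that it does bias the contrast, or that 9-17% is the error rate to expect. The documents do not support either: those figures need three sizeable imbalances in the same direction. About 5-8% is the range for balanced to mildly imbalanced covariates of this strength, and about 8-9% applies without any confounding if continuous age is a candidate and terms are dropped from the full model. Nor should the rule be read as damaging the main SR v HS comparisons, which do not materially change with complete pairs. Group sizes, covariate effects, imbalances and the 0.05 thresholds are all assumed. This is a cheap improvement, not a fatal flaw.

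**What to change.** - In the pooled Aim 4 and Aim 5 models, replace the significance rule with one fixed set for every NIH Toolbox outcome: sex, baseline BMI and race/ethnicity, with sparse race/ethnicity categories collapsed. Leave continuous age out, or centre it within age group.
- Name the adjusted Aim 4 model as the main test of the older v younger part of Hypothesis 4a, and keep the unpaired t-test as supportive.
- Use a fixed set in the Hypothesis 3b regressions too, since they also relate SR minus HS differences to characteristics that vary between people.
- For cognitive results already in press, report the fixed-set model as a labelled sensitivity analysis.

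The cost is SAP wording, some re-analysis of existing data and a few degrees of freedom, which matter most if the older group is very small. No new data are needed.

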We propose a randomized, crossover, outpatient sleep restriction study with 2 phases of 6 wk each. Sixty -six men and pre-menopausal women, age 20-40 y, BMI 20-34.9 kg/m^2, who have at least one parent with BMI >27 kg/m^2 (if participant BMI is 20-24.9 kg/m^2), will be recruited from the New York City area. Participants who will be recruited to participate in this study will habitually sleep 7-9 h/night, will be free of any current and past sleep and psychiatric disorders, including eating disorders, and will not have diabetes or CVD. The sleep durations will be the participant's regular bed- and wake-times during the habitual sleep (HS) phase and HS minus 1.5 h in the sleep restriction (SR) phase. During the HS phase, participants will be asked to follow a fixed bedtime routine based on their screening sleep schedule. During the SR phase, participants will be asked to keep their habitual wake time constant but delay their bedtime to achieve a reduction of 1.5 h in total sleep time. Two weeks prior to randomization and during washout periods, participants will wear an actigraph (Micro Motion Logger Sleep Watch, Ambulatory Monitoring, Inc., Ardsley, NY) and keep a sleep diary to verify sleep duration and sleep-wake schedule. In addition to achieving an average sleep of 7-9 h/night, per wrist actigraphy, participants will only be enrolled if they achieve 7 h of sleep for at least 10 of the 14 nights of screening and have <4 nights with <6 h of sleep. At randomization, a urine pregnancy test (for women) and drug screen will be performed. Participants will be asked to abstain from caffeine and alcohol intake for 24 h prior to the start of each study phase. Between study phases, if participants have not returned to baseline sleep patterns, an additional 2-4 wk washout period will be provided. In general, washout periods will be 6 wk in duration. This washout length enhances the likelihood that women will be in the same phase of their menstrual cycle at the start of each experimental phase. On the first day of each study phase (baseline), participants will come to Irving Center for Clinical and Translational Research (CTSA) at Columbia University in the morning after an overnight, 12-h fast. Participants will have anthropometric measurements taken, will provide a fasting blood sample, and will then be taken to the department of Radiology to undergo MRI scanning to assess body composition. Participants will begin the fixed bedtime routine that night. These baseline measurements will be repeated at endpoint, 6 wk later. Body weight and waist circumference will be measured weekly, fasting blood and urine samples will be taken at baseline, week-3, and endpoint, during adherence check visits. Brain responses will be assessed using two fMRI paradigms (resting state and task-based) at wk 6, 1 h before the participant's self-reported usual dinner time. The resting state paradigm and intrinsic functional connectivity (iFC) analysis will assess treatment effects on reward and interoception-related neuronal circuitry. During the resting state scan (2 runs, each ~ 5 mins), participants will focus on the fixation cross in the center of the screen. Wakefulness and compliance with eyes-open instructions will be monitored via an eye-tracking camera and verbal reminders given before every run. Pulse and respiration rates will be measured using MRI-compatible non-invasive physiological monitoring equipment. Food intake will be assessed at baseline, wk 3, and wk 6 by 3-d food records (2 weekdays and one weekend day) using an electronic app or by hand if the participant does not have a smart phone. EE will be assessed

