Participants will perform tests included in the NIH Toolbox at baseline and week 6 of each study phase. The test battery will be performed in the morning, after an overnight fast, in conjunction with blood sampling. These computerized tests will be supplemented with the ModRey. For this test, participants are read a series of words and asked to recall them during three learning trials, after a brief delay, and after a longer delay. There is also a distractor list and a memory recognition trial. The learning and short delay trials will be administered prior to administration of the NIH Toolbox and the long delay and recognition trials will be administered afterwards. Psychometrically similar alternative forms are available and will be counterbalanced.

Structural brain imaging will be performed at Columbia University Irving Medical Center. This procedure will take place in conjunction with the whole-body scan that is currently performed in the parent study and will only be performed at baseline of phase 1. The protocol derives measures of brain atrophy/volumetry and white matter hyperintensities, but we will also examine microbleeds and infarcts for secondary analyses. Scanning will take place in a single session and include a high-resolution T1-weighted anatomical scan (MPRAGE), T2-weighted FLAIR, and gradient echo (GRE). We will also collect diffusion-weighted imaging and diffusion tensor imaging data for secondary or exploratory analyses. The MRI data will be transferred to a PACS for clinical review and via established, secure DICOM servers the data are also transferred to [name] laboratory for analysis.

---

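### Aim 4 lists carryover as a model term while the general plan tests it and drops it if not significant; the two must be reconciled, and either reading can harm the estimate of the SR effect on cognition within each age group

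*Combined protocol and SAP*

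**What the plan says.** All the analysis text is in the Statistical Procedures section.

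- **Aim 4.** Each NIH Toolbox outcome gets its own mixed model, separately for older and younger participants. The terms are "Sleep (SR vs. HS), along with phase (1 vs. 2), carryover effects, and covariates", with a bracket after the covariates that makes inclusion depend on significance in a first analysis, and "Subject will be used as a random effect".
- **General paragraph.** The plan says "we will test for carryover effects by using a treatment x phase interaction in an initial version of each linear model", and then "If the interaction term is not significant then we will rebuild the linear model without the interaction term". It gives no significance level for that test and no coding for the interaction.
- **Linear Mixed Model Analyses paragraph**, to which Aim 4 refers. Its only removal rule is for covariates.
- **Age-group comparison in Aim 4, and Aim 5.** Both use each person's HS-to-SR difference, with no carryover term.

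The Study Design section gives the structure: "We propose a randomized, crossover, outpatient sleep restriction study with 2 phases of 6 wk each"; "In general, washout periods will be 6 wk in duration"; and "Participants will perform tests included in the NIH Toolbox at baseline and week 6 of each study phase". Each person therefore has up to four scores per Toolbox measure. Aim 4 does not say whether its response is the week-6 score, the change over a phase, or all four values.

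**The concern.** A crossover gains its precision by comparing each person with themselves. In a two-sequence, two-phase design with one response per phase there are only four sequence-by-phase means. A model with intercept, sleep, phase and carryover uses all four, and nothing is left to support a within-person estimate of the SR effect.

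A rule that keeps carryover only when it is significant has a different fault. The carryover test and the phase-1 comparison that replaces the crossover estimate share much of the same data, so a chance imbalance that triggers the first tends also to make the second significant.

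At stake is the first half of Hypothesis 4a: whether SR impairs cognition within each age group. Aims 1, 2a and 3a also have paired t-tests and Wilcoxon tests. The only t-test in Aim 4 is the unpaired one between age groups.

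**Working it through.** **Inputs.** Two sequences and two phases (Study Design); a random subject effect (Aim 4); 50 expected completers (sample size paragraph) and 36 actual completers (Subjects section). Assumed, because the documents do not give them: rho of 0 to 0.8, equal sequence sizes, equal correlations between all scores, two-sided alpha of 0.05.

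**The plan's own figure.** No power is stated for Aim 4. The nearest figure is above 99% for paired t-tests with 50 completers. The effect sizes reproduce as 0.69/0.36 = 1.92 and 0.91/0.65 = 1.40. For the smaller, power is about Φ(1.40 × √50 − 1.96) = Φ(7.94), close to 1. That figure assumes a paired analysis.

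**Reading 1: the term is kept (one response per phase, reference coding).** Write τ for SR, π for phase 2 and λ for carryover.

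| Sequence | Phase 1 | Phase 2 |
|---|---|---|
| SR then HS | μ + τ | μ + π + λ |
| HS then SR | μ | μ + π + τ |

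Four parameters fit four means, so the estimate of τ is the phase-1 difference between the two groups. With n people in total:

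- with λ: variance = 2σ²/(n/2) = 4σ²/n
- without λ: variance = 2σ²(1 − rho)/n
- ratio = 2/(1 − rho), which does not depend on n

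| rho | Ratio | SE without λ (SD units, n = 36) | SE with λ |
|---|---|---|---|
| 0 | 2.0 | 0.236 | 0.333 |
| 0.5 | 4.0 | 0.167 | 0.333 |
| 0.7 | 6.7 | 0.129 | 0.333 |
| 0.8 | 10.0 | 0.105 | 0.333 |

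The effect detectable with 80% power is (1.96 + 0.84) × SE. At n = 36 that is 0.93 SD with the term, against 0.47 SD (rho 0.5) or 0.30 SD (rho 0.8) without it. The 36 completers span both age groups, so each Aim 4 model would have fewer.

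**How far this depends on what the plan leaves open.**

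- Change scores: under equal correlations the two phase changes are uncorrelated, so rho is 0 and the ratio is 2.
- All four Toolbox values modelled: the variance ratio is 1.7 to 1.9 if carryover is the same at the phase-2 baseline and week 6, and 3.0 to 3.6 if it is free at each (rho 0.5 to 0.8).
- Sum-to-zero coding of treatment x phase: the sleep coefficient keeps variance 2σ²(1 − rho)/n, so no precision is lost. It equals the SR effect only if carryover is zero.

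**Reading 2: the pre-test governs (ordinary coding, one response per phase).** The carryover test compares the sequences on each person's total over both phases. The correlation of that total with the phase-1 score is √((1 + rho)/2), which is 0.87, 0.92 and 0.95 at rho 0.5, 0.7 and 0.8. Simulation with n = 36, no carryover and no SR effect gives:

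- Pre-test at 0.05: the term is kept in about 5% of trials. The phase-1 SR test is then falsely significant in 54%, 63% and 68% of them (rho 0.5, 0.7, 0.8). Overall type I error is about 7.6 to 8.0%.
- Pre-test at 0.10: overall type I error is about 8.3 to 8.9%.

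Arithmetic check at 0.05: 0.95 × 0.05 + 0.05 × 0.54 = 0.0745, and 0.95 × 0.05 + 0.05 × 0.68 = 0.0815. A repeat with 400,000 trials per setting gave 7.3%, 7.9% and 8.2% at the 0.05 level and 8.1 to 9.1% at the 0.10 level, so the size is settled to within a few tenths of a percentage point.

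**The case against.** The strongest reply is that Aim 4 should be read under the general paragraph. Its drop rule covers each linear model and Aim 4 does not cancel it. The condition in brackets might also cover carryover, although elsewhere in Aims 4 and 5 the same condition attaches to covariates alone. On this reading the term would usually go. The point stands: a reader might infer that Aim 4 always estimates SR from phase 1 alone, and the documents do not establish that. It does not rescue the plan, because the procedure is then the pre-test of Reading 2.

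Three further replies have force.

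- The 4 to 10-fold figures need one response per phase and ordinary coding. The plan states neither.
- A reader might infer that a term that is always kept would turn chance sequence differences into false SR findings. It would not. The phase-1 comparison is randomized and its SE reflects between-person variance, so type I error stays nominal and the cost is power. The inflated error belongs only to the pre-test.
- Within-person analyses of cognition exist elsewhere. The age-group comparison and Aim 5 use HS-to-SR differences, and the first step of the Aim 6 mediation analysis has sleep as its only fixed effect. They are unaffected, but none is the stated test of the SR effect for Aim 4.

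**Conclusion.** The concern holds in a limited form. Two statements in the Statistical Procedures section disagree on whether carryover stays in the Aim 4 model, and with ordinary coding both readings damage the SR estimate within each age group. Keeping the term costs power: the variance rises 2-fold (change scores) to 10-fold (rho 0.8) with one response per phase, or about 1.7 to 3.6-fold if all four scores are modelled. Pre-testing it costs error control: roughly 7.5 to 8% instead of 5%, or 8 to 9% with a 0.10 pre-test. Sum-to-zero coding avoids the precision loss, but the plan does not specify it.

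These sizes rest on the assumed rho, equal sequences, equal correlations and, for the error rates, 36 participants with no true carryover. The documents do not support the claim that the crossover's precision is certainly lost, or that the whole of Hypothesis 4a is compromised.

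**What to change.** Reconcile the two statements and write one rule for Aim 4:

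1. Name the response, for example the week-6 Toolbox score, and say how the phase baselines are used.
2. In each age group, fit sleep and phase as fixed effects with subject random. Include no carryover term and no carryover pre-test.
3. Report the sleep x phase (carryover) estimate with its confidence interval as a separate sensitivity result that does not decide which model is used. State its coding.

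The cost is a sentence or two in the plan and a re-run. The downside is that the SR estimate then relies on negligible carryover after the washout. The design already makes that assumption, and the Toolbox scores at the phase-2 baseline allow it to be checked by sequence.

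The Renewal Information section says the study is open only for analysis and reporting and that a paper on cognitive function is in press. The investigators should therefore also state which model and which response were used for the results already reported.
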